#### **5.2.2.8 End of DLT Period (Phase 1a Dose Escalation cohorts only)**

For Phase 1a patients in the combination dose escalation cohorts, if at the end of the DLT period the Investigator determines that the patient may benefit from continued dosing with cabiralizumab and nivolumab, entry into the Extended Treatment Period may be offered.

If the patient continues onto the Extended Treatment Period, proceed to procedures outlined in Section 5.2.2.9.

If the patient does not qualify to receive further study drug, the patient will return to the clinic for the End-of-Treatment Visits outlined in Section 5.2.2.11.

#### **5.2.2.9 Extended Treatment – Subsequent Cycles, Day 1**

Phase 1a extended treatment for patients in combination dose escalation cohorts may begin on Cycle 3, Day 1.

At each infusion visit, patients are to remain at the study site after each administration of cabiralizumab and nivolumab until completion of all post-dose assessments for safety monitoring. The following assessments will be performed at each visit unless otherwise noted ([Appendix B](#)) (a  $\pm$  2 day window is allowed for Day 1 in subsequent cycles post Cycle 1, Day 1):

- Prior to each infusion of study drug (within 72 hours unless otherwise stated):
  - Physical examination including weight
  - Vital signs (blood pressure, pulse, respiratory rate, pulse oximetry and temperature in resting position after 5 minutes rest)
  - ECOG performance status evaluation
  - Clinical safety labs (as described in [Appendix B](#); results must be reviewed before dosing)
  - Collect sample if the patient is being followed for a tumor marker (e.g. CA-125, or others) on Cycle 3 Day 1, then every other cycle after, or as clinically indicated
  - Radiological imaging: CT or MRI scan performed every 8 weeks ( $\pm$  7 days) from the first dose for the first 12 months for patients who remain on treatment (and every 12 weeks ( $\pm$  7 days) thereafter) and 28 days ( $\pm$ 7 days) after the last dose of study treatment.
  - Serum pregnancy test ( $\beta$ -hCG) for women of childbearing potential on Cycle 5, Day 1, then every 8 weeks (every 4 cycles)
  - Skin and tumor biopsy collection (prior to Cycle 3 only; within 7 days prior to Cycle

- 3 Day 1 and at least 24 hours prior to dosing; analyses described in [Appendix D](#))
- Optional skin and tumor biopsy for patients who responded to treatment (within 14 days post tumor assessment; for analyses described in [Appendix D](#))
  - Blood collection for:
    - Serum (analyses described in [Appendix D](#)) as listed below.
      - Cabiralizumab PK for Cycles 3, 4, 5, 8, 9, 13, and 21, then every 6 cycles while on treatment
      - Nivolumab PK for Cycles 3, 4, 5, 8, 9, 13, and 21
      - Cabiralizumab ADA for Cycles 3, 4, 5, 8, 9, 13, and 21, then every 6 cycles while on treatment
      - Nivolumab ADA for Cycles 3, 4, 5, 8, 9, 13, and 21
      - ANA for Cycles 3, 4, 5, 9, 13, and 21, then every 6 cycles while on treatment
      - Selected serum markers for Cycles 3, 4, 5, 8, 9, 13, and 21
      - Cytokine multiplex panel for Cycles 3, 4, 5, 8, 9, 13, and 21
    - Whole blood (for analyses described in [Appendix D](#)) as listed below.
      - CD14+/CD16+ monocytes for Cycles 3, 4, 5, 8, 9, 13, and 21, then every 6 cycles while on treatment
      - Gene expression analysis for Cycles 3, 5, 9, 13, 17, and 21, then every 6 cycles thereafter
      - Frozen PBMC for Cycle 3 (analyses described in [Appendix D](#))
  - AE reporting, if applicable
  - Review of concomitant medications
  - Study drug administration: Nivolumab will be given first, with a 30- to 60-minute rest, followed by cabiralizumab.
    - Nivolumab administered by IV infusion over 30 minutes ( $\pm$  5 minutes) (If any Grade 3 or higher infusion reaction is observed during the proposed infusion rate of nivolumab 3 mg/kg over 30 minutes, the infusion rate will be extended to 60 minutes for all current and subsequent patients for the duration of this study)
      - Post-nivolumab administration during the 30- to 60-minute rest:
        - Post-dose vital signs (blood pressure, pulse, respiratory rate, and temperature in resting position after 5 minutes rest) at the following time point after completion of each IV infusion:
          - 10 ( $\pm$ 5) minutes
        - Blood collection for serum (for analyses described in [Appendix D](#)) as listed below.
          - 15 minutes ( $\pm$ 5 minutes) Nivolumab PK for Cycle 8 only

- Cabiralizumab administered by 30 minutes IV infusion ( $\pm$  5 minutes)
  - Post- cabiralizumab administration:
    - Post-dose vital signs (blood pressure, pulse, respiratory rate, and temperature in resting position after 5 minutes rest) at the following time points after completion of cabiralizumab IV infusion:
      - 10 ( $\pm$ 5) minutes, 30 ( $\pm$ 10) minutes, and 60 ( $\pm$ 15) minutes
    - Blood collection for serum (for analyses described in [Appendix D](#)) as listed below.
      - Cabiralizumab PK 15 minutes ( $\pm$ 5 minutes) for Cycles 3 and 4
      - Cabiralizumab PK 15 minutes ( $\pm$ 5 minutes), 4 hours ( $\pm$ 60 minutes), 24 hours ( $\pm$ 6 hours), 72 hours ( $\pm$ 12 hours) and 168 hours ( $\pm$ 24 hours) for Cycle 8 only
      - Selected serum markers 72 hours ( $\pm$ 12 hours) and 168 hours ( $\pm$  24 hours) for Cycle 8 only
      - Cytokine multiplex panel 72 hours ( $\pm$ 12 hours) and 168 hours ( $\pm$ 24 hours) for Cycle 8 only
      - CD14+/CD16+ monocytes 72 hours ( $\pm$ 12 hours) and 168 hours ( $\pm$ 24 hours) for Cycle 8 only

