  - Grade 4 drug-related endocrinopathy AEs, such as adrenal insufficiency, adrenocorticotrophic hormone (ACTH) deficiency, hyper- or hypothyroidism, or glucose intolerance, which resolve or are adequately controlled with physiologic hormone replacement (corticosteroids, thyroid hormones) or glucose-controlling agents, respectively, may not require discontinuation after discussion with and approval from the Sponsor’s Medical Monitor or designee.
  - Grade 4 CK up to 20 xULN (in the absence of clinical sequelae)
- Any event that leads to delay in dosing lasting > 6 weeks from the previous dose requires discontinuation, with the following exceptions:
  - Dosing delays to manage drug-related adverse events are allowed. Prior to re-initiating treatment in a patient with a dosing delay lasting > 6 weeks from the previous dose, the Sponsor’s Medical Monitor or designee must be consulted. Tumor assessments should continue as per-protocol even if dosing is delayed. Periodic study visits to assess safety and laboratory studies should also continue per protocol, or more frequently if clinically indicated during such dosing delays or per the Investigator’s discretion.

- Dosing delays lasting > 6 weeks from the previous dose that occur for non-drug-related reasons may be allowed if approved by the Sponsor’s Medical Monitor or designee. Prior to re-initiating treatment in a patient with a dosing delay lasting > 6 weeks, the Sponsor’s Medical Monitor must be consulted. Tumor assessments should continue per protocol every 8 weeks ( $\pm 7$  days) even if dosing is delayed. Periodic study visits to assess safety and laboratory studies should also continue per-protocol or more frequently if clinically indicated during such dosing delays or per the Investigator’s discretion.
- Any AE, laboratory abnormality, or intercurrent illness which, in the opinion of the Investigator, presents a substantial clinical risk to the patient with continued cabiralizumab and/or nivolumab dosing
- Any drug-related Grade 3 or higher neurological toxicity
- Any Grade 3 or higher periorbital edema and persistent Grade 2 periorbital edema requiring 2 missed doses unless approved by Sponsor’s Medical Monitor
- Any Grade 3 or higher drug-related diarrhea or colitis, which does not resolve to Grade 1 or baseline within 28 days.
- Any Grade 4 skin toxicity
- Any Grade 4 renal toxicity
- Any drug-related Grade 3 or higher pulmonary toxicity

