#### **4.3.6 Infusion Delays and Missed Doses with Cabiralizumab and Nivolumab**

In case an infusion cannot be administered at a scheduled visit, it must be administered as soon as possible. If the delay is between 1 and 7 days, the procedures at the original scheduled visit should be performed. If the delay is more than 7 days, the infusion at the original scheduled visit will be considered a missed dose and the procedures at the next visit should be performed. If the delay is longer than 7 days, subsequent visits will follow a 2-week (or 3-week in Phase 1a 3-week dosing regimen cohort) dosing interval. If the delay is less than 7 days, the original dosing schedule should be followed. The time between two treatment cycles should be no less than 12 days.

Patients may miss up to up to 6 weeks between doses and may resume the study drug if the event returns to baseline or  $\leq$  Grade 1 within 6 weeks of treatment interruption. Omission of additional dosing longer than 6 weeks for AEs will necessitate the patient’s discontinuation from the study unless allowed by the Sponsor’s Medical Monitor or designee. Patients may miss doses in the

course of participation in the study, including missed doses for scheduled vacations or other personal reasons as needed, but not more than 6 weeks unless approved by the Sponsor's Medical Monitor or designee.

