## 5.2.2 Phase 1a Combination (including 1aC, 1aE, and 1aD cohorts)

### 5.2.2.1 Screening Period (Day –28 to Day 0)

Patients who have consented to participation in the study will undergo screening assessments within 28 days (4 weeks) prior to administration of the first infusion of cabiralizumab and nivolumab (unless otherwise stated). To determine if the patient meets all inclusion criteria and does not violate any exclusion criteria, the following procedures will be performed ([Appendix B](#)):

- Written, signed informed consent must be collected prior to any study-specific procedures
- If available, collect an FFPE tissue block or 10 slides of archival tumor sample
- Complete medical and disease history including prior HPV status
- Demographic and baseline characteristics
- Complete physical examination including height and weight
- Photo of periorbital region (required at screening, and if clinically indicated during the study)
- Vital signs (blood pressure, pulse, respiratory rate, pulse oximetry and temperature in resting position after 5 minutes rest)
- ECOG performance status evaluation

- Screening labs (as described in [Appendix B](#))
- Clinical safety labs (as described in [Appendix B](#))
- Collect sample if the patient is being followed for a tumor marker (e.g. CA-125, or others)
- 12-lead ECG (required at screening, and if clinically indicated during the study)
- Radiological imaging: CT or MRI is to be performed within 28 days prior to Cycle 1 Day 1. If the CT or MRI is performed as part of the patient's standard of care within 28 days of Cycle 1 Day 1, it does not need to be repeated if the documentation of results is provided and is adequate for RECIST v1.1
- Serum pregnancy test ( $\beta$ -hCG) for women of childbearing potential
- Skin and tumor biopsy collection (at least 24 hour prior to dosing; analyses described in [Appendix D](#))
- SAE reporting, if applicable
- Document prior and concomitant medications

#### 5.2.2.2 Cycle 1, Day 1

The following procedures will be performed:

- Prior to cabiralizumab and nivolumab infusion (within 72 hours unless otherwise stated):
  - Verification of eligibility
  - Update medical and disease history to capture any changes from screening
  - Physical examination including weight
  - Vital signs (blood pressure, pulse, respiratory rate, pulse oximetry and temperature in resting position after 5 minutes rest)
  - ECOG performance status evaluation

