**Appendix A: Schedule of Assessments – Phase 1a Cabiralizumab Monotherapy and Combination**

Procedure a	Screening	Cycle 1					Cycle 2	Cycle x s	Cycle 8	End-of-Treatment Follow-up Period	Long-Term Follow-up Period u
	Day -28 to Day 0	Day 1 b	Day 2	Day 4	Day 8	Day 15 c	Day 1 b	Day 1 b	Days 2, 4, 8 (and 15) c	28 (±7) days and 100 (±7) days post-last dose	
Informed Consent	x										
Review/Confirm Eligibility Criteria	x	x									
Medical History / Demographics	x	x									
Physical Examination d	x	x			x	x c	x	x	x c	x	
Height and Weight e	x	x					x	x		x	
Vital Signs f	x	x			x	x c	x	x	x c	x	
Photo of Periorbital Region	x										
ECOG Performance Status g	x	x					x	x		x	
Screening Labs h	x										
Clinical Safety Labs i	x	x			x	x c	x	x	x c	x	
12-Lead ECG j	x									x	
CT or MRI Tumor Assessment k,l	x							x		x	x
Serum Pregnancy Test m	x	x						x		x	
Skin and Tumor Biopsy n	x							x		x	
PK Sampling o,p		x	x	x	x	x c	x	x	x	x	
PD Sampling o		x		x	x		x	x	x	x	
ADA Sampling o		x					x	x		x	
ANA Sampling q		x					x	x		x	
Study Drug(s) r,s		x					x	x			
Adverse Events	x-----x										
											
Long-Term Follow-up Contact u											x

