**Notes for Phase 1a Schedule of Assessments**

- a. Unless specified, prior to infusion procedures are to be completed within 72 hours of scheduled time point and to be synchronized with administration of assigned study drug. Any clinical assessment, laboratory study, or additional non-specified tests may be obtained at any time, if clinically indicated.
- b. Each cycle will be 14 days long, with administration of cabiralizumab ± nivolumab on Day 1. In Cohort 1aD, each cycle will be 3 weeks long, with administration of cabiralizumab and nivolumab on Day 1. The first day of treatment in Cycle 1 is defined as Day 1; a ± 2 day window is allowed for Day 1 in subsequent cycles.
- c. Day 15 Assessments (Physical Examination, Vital Signs and Clinical Safety Lab) will apply to patients in Cohort 1aD only
- d. Standard physical examination will be performed as determined by the Investigator, particularly to follow physical findings to resolution. Targeted physical exams should be conducted at any time to follow up on AE reports.
- e. Height is only required to be recorded at screening. Weight is required to be recorded at Day 1 of each cycle. Dose will be adjusted only if weight change is >10% from first dose on Cycle 1 Day 1.
- f. Vital signs include pulse, respiratory rate, blood pressure, and temperature in the resting position (sitting or supine). Measure prior to dose and after completion of each IV infusion at the following time points: 10 (±5) minutes, 30 (±10) minutes, and 60 (±15) minutes, 168 hours (±24 hours) [Cycle 1 only] post cabiralizumab administration; 10 (±5) minutes post nivolumab administration. Pulse oximetry is performed at rest prior to dosing for the combination cohorts only.
- g. Patient ECOG Status assessments are to be performed within 72 hours prior to dosing (Day 1 of each cycle).
- h. Screening labs include serology for Hepatitis B (HBsAg), Hepatitis C (HCV antibody), and test for latent TB (e.g. T-SPOT, Quantiferon).
- i. Clinical Safety Labs:
  - Hematology** including CBC with differential, platelets, hemoglobin, hematocrit, RBC, and RBC indices

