  - Chemistry** includes CK (creatinine kinase), AST (aspartate transaminase), ALT (alanine transaminase), alkaline phosphatase, bicarbonate, bilirubin, (direct and total), BUN (blood urea nitrogen), calcium, chloride, creatinine, glucose, LDH (lactate dehydrogenase), phosphorus, potassium, sodium, and, if applicable, serum pregnancy. Albumin, amylase, lipase, thyroid panel includes TSH, Free T3 and Free T4, PT/INR, and PTT (aPTT) perform at Screening and as indicated. If CK elevation is clinically significant, obtain troponins (cardiac and skeletal), CK isoenzymes, aldolase, and ECG; repeat CK and these additional tests within 48 hours or other interval as clinically indicated, until resolved or stable. If either AST or ALT is elevated, obtain total serum bilirubin, alkaline phosphatase; repeat within 48 hours or other interval, as clinically indicated, until resolved or stable. Additional tests may be obtained at any time, if clinically indicated. If a patient is being followed for a tumor marker (e.g. CA-125, or others), a sample for the tumor marker should be obtained at screening and every other cycle, or if clinically indicated during the study
  - Urinalysis:** Urine dipstick will only be done at screening, and when clinically indicated.
- j. Obtain ECG records at Screening and the Day 28 post last infusion End-of-Treatment Visit (after PK blood draw, record exact time). Additional ECGs should be obtained at any time, if serum CK or cardiac troponin is elevated; if abnormal (excluding sinus tachycardia), ECGs should be obtained (if clinically indicated), until the abnormality is resolved or clinically stable. Additional ECGs may be obtained at any time, if clinically indicated. ECGs for each patient should be obtained from the same machine whenever possible. To minimize variability, it is important that patients be in a resting position for at least 5 minutes prior to each ECG evaluation. Body position should be consistently maintained for each ECG evaluation to prevent changes in heart rate. Environmental distractions (e.g., television, radio, conversation) should be avoided during the pre-ECG resting period and during ECG recording.

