- k. CT or MRI of the Tumor sites measured as per Response Evaluation Criteria in Solid Tumors (RECIST v1.1). If patient terminates prior to scheduled CT or MRI scans, patient should have scans done at End-of-Treatment Visits (does not need to be repeated if performed within 8 weeks prior to End-of-Treatment Visits or if tumor progression was previously determined). Patients who enter Long-Term Follow-up while showing clinical benefit should have tumor assessments q12w for duration of response. The same measuring modality should be used by the site to maintain consistency across the various time points. (Documentation of skin lesions by color photography, including a ruler to measure the size of the lesion, is suggested and should follow the CT or MRI schedule.) Brain scans will be required only if CNS metastasis is suspected, based on Investigator clinical judgment (except for patients in cohort 1b7).
- l. Performed every 8 weeks (±7 days) from the first dose for the first 12 months for patients who remain on treatment (and every 12 weeks (±7 days) thereafter) and 28 days (± 7 days) after the last dose of study treatment. CT or MRI scans do not need to be repeated if performed within 8 weeks prior to the End-of-Treatment Visits or if tumor progression was previously determined.
- m. All women of childbearing potential will have a serum pregnancy test at screening, Cycle 1 Day 1 and every 8 weeks during treatment, and at the End-of-Treatment Visits.
- n. Biopsy at primary tumor or metastatic tumor site and skin biopsy from a site devoid of disease (e.g. rash or urticaria) will be collected at screening [at least 24 hours prior to dosing] and prior to Cycle 3 Day 1 [within 7 days prior to Cycle 3 Day 1 and at least 24 hours prior to dosing]. It is recommended that patients who have documented response receive another biopsy within 28 (±14) days post tumor assessment and/or patient who have progression receive another biopsy at the final End-of-Treatment visit. The post-response and post-progression biopsies are optional. If available, collect an FFPE tissue block or 10 slides of archival tumor sample at Screening.
- o. Samples will be collected for PK, PD, and ADA analyses. Not all visits will require collection of all three – see [Appendix C](#) for collection schedule.

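### The pregnancy-test line in Protocol Section 5.2.2.9 fits only 14-day cycles; in cohort 1aD (21-day cycles) it contradicts its own 8-week interval and both schedule appendices

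*Protocol*

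**What the plan says.** The heading of Protocol Section 5.2.2 reads "Phase 1a Combination (including 1aC, 1aE, and 1aD cohorts", closing the bracket there, so its subsections apply to 1aD unless they say otherwise. Section 5.2.2.9 describes Day 1 visits in later cycles and sets the pregnancy test "for women of childbearing potential on Cycle 5, Day 1, then every 8 weeks (every 4 cycles".

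Appendix A note b gives the cycle length: "In Cohort 1aD, each cycle will be 3 weeks long". All other cohorts use 14-day cycles.

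The test interval also appears in both schedules. Appendix A (Phase 1a), note m: "All women of childbearing potential will have a serum pregnancy test at screening, Cycle 1 Day 1 and every 8 weeks during treatment". Appendix B note l gives the same 8-week interval while on treatment. Appendix B is titled for Phase 1b, but it is the schedule that Section 5.2.2.9 links to. Neither note makes an exception for 1aD, and neither states a window around the 8 weeks.

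The chemistry panel in Appendix A note i includes "if applicable, serum pregnancy" without an interval. The separate "Serum Pregnancy Test" row in Appendix A has no mark at Cycle 2 Day 1.

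**The concern.** The line states one rule in two units, weeks and cycles, and treats them as equal. They are equal only when a cycle lasts 14 days. In 1aD the cycle wording gives a later first test and a longer repeat interval than the weeks wording beside it, so two sites could follow the same line and test on different dates.

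The test has consequences for the patient. Pregnancy requires study drug to stop (Sections 3.4 and 6.5) and is handled as a serious adverse event (Section 6.2). A later test means a later chance to detect a pregnancy, with one more infusion of both antibodies given before it.

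**Working it through.** **Inputs.** Cycle length L: 14 days, or 21 days in 1aD (Appendix A note b). Test rule: Section 5.2.2.9. Reference interval: 8 weeks = 56 days (Appendix A note m, Appendix B note l). All dates are nominal, with no dose delay.

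**Formulas.** Cycle k Day 1 falls on day 1 + (k − 1) × L. An interval of n cycles is n × L / 7 weeks.

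**The plan's own equivalence, 14-day cycles.** Cycle 5 Day 1 = 1 + 4 × 14 = day 57, which is 8 weeks after first dose. Four cycles = 4 × 14 / 7 = 8 weeks. The line is consistent.

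**The same line in 1aD, 21-day cycles.** Cycle 5 Day 1 = 1 + 4 × 21 = day 85, which is 12 weeks after first dose. Four cycles = 4 × 21 / 7 = 12 weeks. Eight weeks = 56 / 21 = 2.67 cycles, so no whole number of 1aD cycles equals the stated interval.

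**Difference at the first on-treatment test.** 85 − 57 = 28 days. Infusions before day 57: days 1, 22 and 43, so three. Infusions before the pre-dose test on day 85: days 1, 22, 43 and 64, so four.

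**On-treatment tests in 1aD up to day 169 (24 weeks after first dose):**

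| Rule followed | Test days | Number |
|---|---|---|
| Either appendix, every 8 weeks | 57, 113, 169 | 3 |
| Section 5.2.2.9, then every 4 cycles | 85, 169 | 2 |
| Section 5.2.2.9, then every 8 weeks | 85, 141 | 2 |
| Cycle 3 Day 1, then every 2 cycles | 43, 85, 127, 169 | 4 |
| Dosing visits nearest the 8-week points (Cycles 4, 6, 9) | 64, 106, 169 | 3 |

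**Which dosing-visit schedule respects 8 weeks.** Testing every 2 cycles gives gaps of 2 × 21 = 42 days. With the ±2-day visit window the largest gap is 42 + 2 + 2 = 46 days, below 56. The Cycles 4, 6 and 9 schedule gives gaps of 64 − 1 = 63, 106 − 64 = 42 and 169 − 106 = 63 days, so two of the three exceed 56.

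**Effect of a delayed dose.** Under Section 4.3.6, an infusion more than 7 days late "will be considered a missed dose and the procedures at the next visit should be performed". Suppose the Cycle 3 infusion is 8 days late (day 43 + 8 = 51) and the visit runs as Cycle 4. The Cycle 3 test is then skipped, and Cycle 5 falls on day 51 + 21 = 72, which is 71 days after first dose. Any test tied to a cycle number therefore needs a calendar limit as well.

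**The case against.** The strongest reply is that the plan already gives the right interval. Both appendices say 8 weeks, and Section 5.2.2.9 itself sends the site to Appendix B. The weeks wording in the line also says 8 weeks. On that view the bracketed cycles are only a gloss, and day 85 arises only if a site ignores both appendices. Much of this stands: it shows what was intended, and it keeps the point small. It does not explain away the first test, which the line ties to Cycle 5 Day 1. Reading the bracket as a gloss leaves day 85 in place. A site could satisfy all the texts by testing at week 8 and again at Cycle 5, but nothing tells it to.

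A second reply is that the opening sentence of Section 5.2.2.9 mentions only the dose-escalation combination cohorts. That sentence says only when extended treatment may begin. Where a subsection is limited to dose escalation, its title says so, as in Section 5.2.2.8. The subsections written for 1aD alone cover Day 15 visits, so excluding 1aD here would leave it with no visit text for Day 1 from Cycle 3 onward.

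A third reply is that the chemistry panel already covers pregnancy before each dose. The panel item is conditional and has no interval. Safety labs are marked at Cycle 2 Day 1 while the pregnancy row is not. That leaves the panel ambiguous, so it cannot settle the timing.

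A reader might also infer more than the documents support:

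- That 12-week testing was chosen for 1aD. The same line appears in the monotherapy and Phase 1b visit text (Sections 5.2.1.8 and 5.2.3.7), where every cycle is 14 days, and 1aD came in with amendment 4 (Section 3.1.2.3). It looks like wording carried over, and both appendices contradict a chosen 12 weeks.
- That 1aD patients receive more untested infusions than the plan accepts elsewhere. Four infusions also precede the Cycle 5 test in the 14-day cohorts (days 1, 15, 29 and 43).
- That women in 1aD are left unprotected. Tests at screening and Cycle 1 Day 1 are required, contraception is mandatory (Section 3.2.2, criterion 11), and extra tests are allowed whenever clinically indicated (Appendix A note a).

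**Conclusion.** The point holds as a minor internal inconsistency in a safety schedule. For 1aD, the cycle wording in Section 5.2.2.9 conflicts with the 8 weeks in the same line, in Appendix A note m and in Appendix B note l. A site following the cycle wording would test first on day 85 instead of about day 57: 28 days late, and after four infusions instead of three. Its repeat interval would be 84 days, or 56 days if it then followed the weeks wording.

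These figures assume nominal visits without dose delays. Cohort 1aD has about 10 patients. The number of women of childbearing potential among them is not given and may be zero. SAP Section 7.6.13 only lists pregnancy results, so no endpoint, estimate or dose decision changes.

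**What to change.** In Section 5.2.2.9, limit the Cycle 5 start and the four-cycle repeat to cohorts with 14-day cycles, and add:

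*Cohort 1aD: at least every 8 weeks from first dose, before dosing on Cycle 3 Day 1 and every 2 cycles thereafter (every 6 weeks). If a dose delay would make the gap exceed 8 weeks, test at the 8-week scan or another visit within that time.*

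The scan is a sensible fallback because it is timed from first dose and Section 4.3.5 keeps it going: "Tumor assessments should continue as per-protocol even if dosing is delayed". After the first 12 months scans move to every 12 weeks, so another visit must then serve.

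The cost is nominally four on-treatment tests instead of the appendices' three over the first 24 weeks, drawn with safety labs already taken at those visits. Neither appendix note needs to change. Testing at Cycles 4, 6 and 9 would keep the count at three, but it breaks the 8-week rule twice and would be acceptable only if note m were given an explicit window.
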